18.2 AJCC 8th Edition TNM Definitions for Pathologic Staging

a. **Table 1 TNM Definitions for Stage III Melanoma: Pathologic Staging**

Stage	TNM	Description
IIIB	T0	No evidence of primary tumor (e.g., unknown primary or completely regressed melanoma)
	N1b	One clinically detected node without micrometastasis
	N1c	No regional lymph node disease with in-transit, satellite, and/or microsatellite metastases
	M0	No evidence of distant disease
IIIC	T0	No evidence of primary tumor (e.g., unknown primary or completely regressed melanoma)
	N2b	2-3 regional lymph nodes, at least one of which was clinically detected without in-transit, satellite, and/or microsatellite metastases
	N2c	One clinically occult or clinically detected regional lymph node with in-transit, satellite, and/or microsatellite metastases
	N3b	4 or more regional lymph nodes, at least one of which was clinically detected, or presence of any number of matted nodes without in-transit, satellite, and/or microsatellite metastases
	N3c	2 or more clinically occult or clinically detected regional lymph nodes and/or presence of any number of matted nodes with in-transit, satellite, and/or microsatellite metastases
	M0	No evidence of distant disease
IIIA	T1a/b- T2a	T1a= Melanomas < 0.8 mm in thickness without ulceration
		T1b = Melanomas <0.8 mm in thickness with ulceration; Melanomas 0.8-1.0 mm in thickness with or without ulceration
		T2a = Melanomas >1.0-2.0 mm in thickness without ulceration
	N1a	One clinically occult regional lymph node (i.e., detected by SLN biopsy) without in-transit, satellite, and/or microsatellite metastases
	N2a	2 or 3 clinically occult regional lymph node (i.e., detected by SLN biopsy) without in-transit, satellite, and/or microsatellite metastases
	M0	No evidence of distant disease
IIIB	T1a/b- T2a	T1a= Melanomas < 0.8 mm in thickness without ulceration
		T1b = Melanomas <0.8 mm in thickness with ulceration; Melanomas 0.8-1.0 mm in thickness with or without ulceration
		T2a = Melanomas >1.0-2.0 mm in thickness without ulceration
	N1 b/c or N2b	N1b = One clinically detected regional lymph node without in-transit, satellite, and/or microsatellite metastases
		N1c = No regional lymph node disease with in-transit, satellite, and/or microsatellite metastases N2b = 2-3 regional lymph nodes, at least one of which was clinically detected without in-transit, satellite, and/or microsatellite metastases
	M0	No evidence of distant disease
IIIB	T2b/T3a	T2b = Melanomas > 1.0-2.0 mm in thickness with ulceration
		T3a = Melanomas > 2.0-4.0 mm in thickness without ulceration
	N1a - N2b	N1a= One clinically occult regional lymph node (i.e., detected by SLN biopsy) without in-transit, satellite, and/or microsatellite metastases
		N1b= One clinically detected regional lymph node without in-transit, satellite, and/or microsatellite metastases
		N1c= No regional lymph node disease with in-transit, satellite, and/or microsatellite metastases

Stage	TNM	Description	
		N2a= 2 or 3 clinically occult regional lymph node (i.e., detected by SLN biopsy) without in-transit, satellite, and/or microsatellite metastases	
	M0	No evidence of distant disease	
IIIC	T1a- T3a	T1a = Melanomas < 0.8 mm in thickness without ulceration	
		T1b= Melanomas <0.8 mm in thickness with ulceration; Melanomas 0.8-1.0 mm in thickness with or without ulceration	
		T2a= Melanomas >1.0-2.0 mm in thickness without ulceration	
		T2b= Melanomas > 1.0-2.0 mm in thickness with ulceration	
		T3a= Melanomas > 2.0-4.0 mm in thickness without ulceration	
	N2c or N3a/b/c	N2c= One clinically occult or clinically detected regional lymph node with in-transit, satellite, and/or microsatellite metastases	
		N3a= 4 or more clinically occult regional lymph nodes (i.e., detected by SLN biopsy) without in-transit, satellite, and/or microsatellite metastases	
		N3c= 2 or more clinically occult or clinically detected regional lymph nodes and/or presence of any number of matted nodes with in-transit, satellite, and/or microsatellite metastases	
	M0	No evidence of distant disease	
	IIIC	T3b/T4a	T3b= Melanomas > 2.0-4.0 mm in thickness with ulceration
T4a= Melanomas > 4.0 mm in thickness without ulceration			
Any N ≥N1		N1a= One clinically occult regional lymph node (i.e., detected by SLN biopsy) without in-transit, satellite, and/or microsatellite metastases	
		N1b = One clinically detected regional lymph node without in-transit, satellite, and/or microsatellite metastases	
		N1c= No regional lymph node disease with in-transit, satellite, and/or microsatellite metastases	
		N2a = 2 or 3 clinically occult regional lymph node (i.e., detected by SLN biopsy) without in-transit, satellite, and/or microsatellite metastases	
		N2b = 2-3 regional lymph nodes, at least one of which was clinically detected without in-transit, satellite, and/or microsatellite metastases	
		N2c = One clinically occult or clinically detected regional lymph node with in-transit, satellite, and/or microsatellite metastases	
		N3a= 4 or more clinically occult regional lymph nodes (i.e., detected by SLN biopsy) without in-transit, satellite, and/or microsatellite metastases	
		N3b= 4 or more regional lymph nodes, at least one of which was clinically detected, or presence of any number of matted nodes without in-transit, satellite, and/or microsatellite metastases	
		N3c = 2 or more clinically occult or clinically detected regional lymph nodes and/or presence of any number of matted nodes with in-transit, satellite, and/or microsatellite metastases	
		M0	No evidence of distant disease
IIIC		T4b	T4b= Melanomas > 4.0 mm in thickness with ulceration
		N1a- N2c	N1a= One clinically occult regional lymph node (i.e., detected by SLN biopsy) without in-transit, satellite, and/or microsatellite metastases
			N1b = One clinically detected regional lymph node without in-transit, satellite, and/or microsatellite metastases
	N1c= No regional lymph node disease with in-transit, satellite, and/or microsatellite metastases		
	N2a = 2 or 3 clinically occult regional lymph node (i.e., detected by SLN biopsy) without in-transit, satellite, and/or microsatellite metastases		
	N2b = 2-3 regional lymph nodes, at least one of which was clinically detected without in-transit, satellite, and/or microsatellite metastases		

Stage	TNM	Description
		N2c = One clinically occult or clinically detected regional lymph node with in-transit, satellite, and/or microsatellite metastases
	M0	No evidence of distant disease
IIID	T4b	T4b= Melanomas > 4.0 mm in thickness with ulceration
	N3a/b/c	N3a= 4 or more clinically occult regional lymph nodes (i.e., detected by SLN biopsy) without in-transit, satellite, and/or microsatellite metastases
		N3b= 4 or more regional lymph nodes, at least one of which was clinically detected, or presence of any number of matted nodes without in-transit, satellite, and/or microsatellite metastases
		N3c = 2 or more clinically occult or clinically detected regional lymph nodes and/or presence of any number of matted nodes with in-transit, satellite, and/or microsatellite metastases
	M0	No evidence of distant disease

b. **Table 2 TNM Definitions for Stage IV Melanoma: Pathologic Staging**

IV	Any T, Tis	TX= Primary tumor thickness cannot be assessed (e.g., diagnosis by curettage)
		T0= No evidence of primary tumor (e.g., unknown primary or completely regressed melanoma)
		Tis= Melanoma in situ
		T1a= Melanomas < 0.8 mm in thickness without ulceration
		T1b = Melanomas <0.8 mm in thickness with ulceration. Melanomas 0.8-1.0 mm in thickness with or without ulceration
		T2a = Melanomas >1.0-2.0 mm in thickness without ulceration
		T2b= Melanomas > 1.0-2.0 mm in thickness with ulceration
		T3a= Melanomas > 2.0-4.0 mm in thickness without ulceration
		T3b= Melanomas > 2.0-4.0 mm in thickness with ulceration
		T4a= Melanomas > 4.0 mm in thickness without ulceration
		T4b= Melanomas > 4.0 mm in thickness with ulceration
		M1
	T – primary tumor; N – regional lymph nodes; M – distant metastasis	
Adapted with permission from AJCC: Melanoma of the Skin. AJCC Cancer Staging Manual. 8 th ed. Chicago, IL: Springer 2017, pp. 577-78.		

18.3 Translational Medicine: Pathological Response

Translational medicine study objective(s):

- 1) On the neoadjuvant arm, to estimate the complete pathologic response rate and compare different definitions of partial pathologic response.
- 2) To evaluate associations between pathologic responses and the endpoints of event-free survival and overall survival.

Background:

Pathologic response after neoadjuvant therapy as a surrogate for survival has been studied in breast cancer. However, the reliability of pathologic evaluation is controversial due to differing evaluation methods and definitions, as well as applicability to different subtypes of breast cancer. In melanoma, neoadjuvant therapy has been studied at only a few academic centers; however, collaborative efforts to standardize pathologic evaluation are underway. **S1801** affords an even greater opportunity for this effort and in addition, the opportunity to review a large cohort of neoadjuvant cases and establish guidelines and standardization for pathologic response evaluation.

1. Santa-Maria CA et al. Neoadjuvant Therapy for Early-Stage Breast Cancer: Current Practice, Controversies, and Future Directions *Oncology* 2015.

Statistical Plan:

The feasibility of specimen submission for this aim will be monitored as follows: the feasibility of obtaining full surgical specimens will first be evaluated after the first 10 participants are enrolled on the neoadjuvant arm. If difficulty exists at the site level releasing complete surgical specimens, SWOG will work with the local PIs to determine barriers and facilitate tissue release. The study team will continue to review and potentially modify the central path review specimen submission procedures until at least 85% of specimens are submitted. If this rate is not achieved in 20 consecutive participants (so 17/20 participants providing specimens) by the time 120 participants have undergone surgery on the neoadjuvant arm, the study team will re-visit the use a sub-study at a limited number of institutions for this objective.

The pathologic complete response (pCR) rate will be estimated on the neoadjuvant arm and exact 95% confidence intervals will be calculated. There is no current consensus definition of pathologic partial response (pPR). Some authors have proposed < 50% viable tumor, though others have argued that 40% necrosis should be considered a partial response. We will use the minimum p-value approach (Mazumdar and Glassman, *Statistics in Medicine*, 2000) to evaluate potential cut-points in percent viable tumor with respect to the outcome EFS for definitions of partial response. In addition, we will use Cox regression models to evaluate the association between the quantitative value of percent viable tumor and overall and event-free survival. We will use C-statistics to estimate the predictive ability of the quantitative and categorical versions of the data. In addition, associations between pCR and pPR (using the definition derived using EFS) and the outcome of overall survival will be assessed with log-rank tests and Cox regression models,

Laboratory conducting the testing:
The University of Texas MD Anderson
Department of Pathology, Immunohistochemistry Laboratory
Contact for this trial: [name]., Ph.D.
[name]
[name]
[name]

Central review is essential to determine the extent of pathologic response in the post-treatment surgical excision specimens.

For this, the following are required from the surgical specimens for central review:

- all tissue blocks, OR
- two (2) unstained FFPE slides per block, OR
- one (1) H&E slide and one (1) unstained slide per block

To the extent that a consistent determination of pathologic response also correlates with pathologic response in other cancer types (notably breast), an accurate and consistent determination of pathologic response is critical.

A critical variable to a consistent pathologic review is consistent pathologic submission guidelines to ensure that the post-treatment surgically resected tumor bed has been adequately sampled when determining pathologic response.

Gross evaluation of the surgical specimen

For the most part, neoadjuvant trials in melanoma have been directed towards surgically resectable nodal disease. As such, the surgical specimen typically consists of regional lymphadenectomy specimens; however, for other specimen types, the same rules as below would apply. Gross examination of the excised regional lymph node basin should seek to identify all possible lymph nodes (including both grossly positive and negative nodes). Three dimensional measurements of all of the grossly positive nodes should be recorded, as the dimensions of the largest involved lymph node will direct subsequent tissue processing.

Histologic assessment by [name]:

- (1) The largest contiguous viable deposit of metastatic melanoma (if there is viable tumor) will be recorded in two dimensions. This will be limited to contiguous viable tumor cells and will not include tumoral melanosis.
- (2) The percentage of the entire apparent tumor bed surface area occupied by viable tumor will be designated as % Viable tumor.
- (3) Viable extracapsular extension of melanoma tumor cells will be recorded as present or absent. If there is evidence of completely regressed extracapsular extension, then the extracapsular extension will be noted as "Present" (completely regressed)
- (4) In addition, evidence of treatment effect will be recorded, including any of the following features and the relative percentages of each:
 - (a) tumor necrosis (% of tumor bed)
 - (b) tumoral melanosis and/or (% of tumor bed)
 - (c) fibrosis (% of tumor bed)

Results of the testing will not be provided to the treating physicians or the participants.

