1.0 OBJECTIVES

- 1.1 Primary Objective(s)
 - a. To compare event-free survival (EFS) in participants with high-risk resectable melanoma randomized to neoadjuvant pembrolizumab (MK-3475) with participants randomized to adjuvant pembrolizumab (MK-3475).
- 1.2 Secondary Objective(s)
 - a. To assess the frequency and severity of toxicities on each of the arms.
 - b. To compare between arms overall survival (OS), disease control at 24 weeks, locoregional control in the surgical site(s), and total number of pembrolizumab (MK-3475) doses received.
 - c. On the neoadjuvant arm, to estimate the pathologic response rate, the RECIST 1.1 response rate (confirmed and unconfirmed CR and PR), and the iRECIST response rate (confirmed and unconfirmed CR and PR), before surgical resection; to compare definitions of pathologic partial response; and to evaluate the association between pathologic response and EFS and OS.
 - d. To describe the proportion of participants on each arm who received the surgery planned at randomization.
- 1.3 Additional Objective(s)
 - a. To bank tumor tissue and whole blood in anticipation of future correlative studies in this participant population. Such proposed analysis includes deep immune profiling, with evaluation of CD3, CD8, PD-L1, CD20, whole exome sequencing studies, and RNA analysis.

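### Section 18.3 aims to compare definitions of pathologic partial response, but plans no analysis of the 40% necrosis definition and no interval for the difference between any two definitions

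*Combined protocol and SAP*

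**What the plan says.** The objective appears twice. Section 1.2, item c, lists, for the neoadjuvant arm, "to compare definitions of pathologic partial response". Objective 1 of Section 18.3 is to estimate the complete response rate and "compare different definitions of partial pathologic response".

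The Statistical Plan in Section 18.3 says there is no consensus on partial response and gives two positions: "Some authors have proposed < 50% viable tumor, though others have argued that 40% necrosis should be considered a partial response". The planned analyses are then:

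- "We will use the minimum p-value approach" "to evaluate potential cut-points in percent viable tumor with respect to the outcome EFS for definitions of partial response";
- Cox models relating quantitative percent viable tumor to EFS and OS;
- "We will use C-statistics to estimate the predictive ability of the quantitative and categorical versions of the data";
- log-rank tests and Cox models for OS, using pCR and the pPR definition that the EFS search produced.

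The histologic assessment in the same section scores viable tumor as a percentage of the tumor bed. Item 4 separately scores "tumor necrosis (% of tumor bed)", tumoral melanosis and fibrosis. Section 10.6 defines path PR as under 50% viable tumor.

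**The concern.** The objective asks whether one definition of partial response is better than another. The null hypothesis of a minimum p-value search, even when correctly adjusted for the number of cuts tried, is that percent viable tumor is unrelated to EFS at every cut. Rejecting it does not show that the selected cut is better than 50%, or better than a definition based on something else.

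The necrosis definition is named as a competing position and its data are collected, yet no planned model uses it. Section 18.3 presents the cohort as an opportunity to set guidelines for scoring response. A cut selected from few events, and never set against the named alternative, would be a weak basis for that.

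**Working it through.** The plan states no alpha, power or precision for this search, so there is no figure to reproduce. The check has four steps.

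**1. Can a viable-tumor cut stand in for 40% necrosis?** Read 40% necrosis as at least 40% of the bed, and treat the scored components as non-overlapping shares. Then viable + necrosis ≤ 100, so necrosis ≥ 40 implies viable ≤ 60. The reverse fails because fibrosis and melanosis also fill the bed. Two specimens show it:

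- A: 30% viable, 20% necrosis, 50% fibrosis. It meets <50% viable but not ≥40% necrosis.
- B: 55% viable, 40% necrosis, 5% fibrosis. It meets ≥40% necrosis but not <50% viable.

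Any viable-tumor cut that counts B as a responder (above 55%) also counts A as one. No cut reproduces the necrosis definition.

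**2. How many events are available?** Section 11.3 plans 336 eligible patients, so 168 on the neoadjuvant arm under 1:1 randomization. Section 18.3 aims for 85% specimen submission: 168 × 0.85 ≈ 143. Section 11.2 expects 104 EFS events across both arms.

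- Equal split: 104/2 × 0.85 = 44.
- Rough split at the design hazard ratio of 0.64: 104 × 0.64/1.64 ≈ 41, and 41 × 0.85 ≈ 35.

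The range is about 35 to 44. It could be lower, because Section 10.10 counts most participants without surgery as events and they supply no surgical specimen.

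**3. What does a significant search result tell us?** Illustrative simulation with 143 specimens and about 40 events. All of these inputs are assumed: 25% pCR; viable percent otherwise uniform; necrosis a Beta(2,2) share of the non-viable bed; exponential EFS times with follow-up of 0.5 to 3.5 years; cuts every 5% with at least 10% of patients on each side; and a 5% critical value for the maximum log-rank chi-square taken from a simulated null. There were 1,500 runs per scenario. In each cell the first figure is for HR 2 and the second for HR 3. In the smooth pattern the log-hazard rises by 1.5 × ln(HR) from 0% to 100% viable, a hazard ratio of 2.8 or 5.2 over the full range.

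| True pattern | Search rejects | Selected cut in 45–55% | 10th–90th percentile of selected cut |
|---|---|---|---|
| Step at 50% viable | 51% / 85% | 43% / 62% | 30–80 / 40–70 |
| Smooth, no threshold | 54% / 89% | 18% / 23% | 20–80 / 30–80 |
| Step at 40% necrosis | 16% / 29% | 18% / 20% | 10–80 / 10–80 |

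The rejection rate is nearly the same whether or not a threshold exists. When necrosis is the driver, the search usually finds nothing. The two named definitions classify about 30% of these simulated patients differently. With 168 specimens and about 47 events, above the range in step 2, the rejection rates are 63% to 93% (smooth) and 22% to 37% (necrosis), so the picture does not change.

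**4. Could a direct comparison be made?** In the same simulation (400 runs per scenario), the mean difference in C favours <50% viable by 0.042 / 0.066 when that is the true driver, and ≥40% necrosis by 0.028 / 0.045 when necrosis is. The SD of the difference is about 0.04, so a 95% interval has a half-width of about 1.96 × 0.04 = 0.078. That exceeds every one of these means. The comparison is feasible but imprecise.

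**The case against.** The strongest case against is that the plan does more than test for association. A minimum p-value search also ranks cuts, and 50% can be among them. The Cox models on quantitative viable tumor and the planned C-statistics allow a descriptive comparison of cut-based against continuous viable tumor, which bears directly on the smooth-risk case. Rejecting when viable tumor really does predict EFS is a correct finding of association. All of this stands. A reader might infer that the comparison of definitions is left wholly unanswered; for viable-tumor cuts the documents do not support that.

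A reader might also infer that the searched cut becomes the trial's definition of partial response, or that the plan treats a small minimum p-value as proof of superiority. Neither is supported. Section 10.6 keeps the 50% definition, Section 18.3 carries the EFS-derived cut only into OS association analyses, and the plan never claims superiority for the selected cut. The primary analysis does not depend on it.

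The objectives also list no definitions, and the authors may have meant necrosis loosely as the non-viable share of the bed. That is possible, but the text does not say so, and the histologic scoring keeps the components apart.

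Finally, the size of the necrosis problem depends on an assumed prevalence and effect that the documents do not give. This also stands. If few specimens reach 40% necrosis, a direct analysis would have little power too.

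**Conclusion.** The concern holds in limited form. The plan can rank viable-tumor cuts descriptively, but it never compares viable tumor with necrosis, specifies no contrast between definitions with an interval, and carries only the EFS-derived cut to OS. These conclusions follow from the text and from the counterexample in step 1; they do not need the simulation.

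The simulation shows only the mechanism. At about 40 events and HR 2 to 3, the adjusted search rejects in about 54% to 89% of runs with smooth risk and no threshold, and in about 16% to 29% when 40% necrosis is the driver. These figures rest on assumed pCR, viable-tumor and necrosis distributions and assumed effect sizes. What is affected is a secondary objective.

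**What to change.** In the Statistical Plan of Section 18.3:

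- List the definitions to be compared: <50% viable tumor, ≥40% necrosis (already scored under item 4a), and the data-derived viable-tumor cut. If 40% necrosis was meant as a statement about viable tumor, say so.
- Fit each definition separately to EFS and OS, and report its hazard ratio and C-statistic.
- Report paired-bootstrap differences in C between definitions with 95% intervals, repeating the cut selection inside each bootstrap sample so that the data-derived cut gains no unfair advantage.
- Keep the minimum p-value search as exploratory, give a bootstrap interval for the selected cut, and state that significance shows association with EFS only. State whether pCR specimens enter the search.

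The cost is some SAP wording and a few more models on data already collected. The downside is a more modest conclusion: with an SD of about 0.04 for the difference in C, the intervals will often include zero.

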10.6 Pathologic Response

In prior studies using neoadjuvant targeted (BRAF/MEK inhibitor) and neoadjuvant immune checkpoint blockade therapy, previously agreed upon standard definitions of pathologic response are:

- **Complete pathologic response (path CR):** the complete absence of viable tumor cells in the surgically resected post-treatment specimen.
- **Partial pathologic response (path PR):** admixture of viable tumor cells but these comprise less than 50% of the treated tumor bed surface area together with evidence of treatment effect, including necrosis, fibrosis, and a lymphohistiocytic inflammatory infiltrate including aggregates of pigmented macrophages (tumoral melanosis).
- **Pathologic non-response (path NR):** admixture of viable tumor cells and these comprise greater than 50% of the treated tumor bed surface area together with evidence of treatment effect, including necrosis, fibrosis, and a lymphohistiocytic inflammatory infiltrate including aggregates of pigmented macrophages (tumoral melanosis).

10.7 **IRECIST Objective status at each disease evaluation:**

Objective Status is to be recorded at each evaluation. All measurable lesions up to a maximum of 2 lesions per organ 5 lesions in total, representative of all involved organs, should be identified as *target* lesions at baseline All other lesions (or sites of disease) including any measurable lesions over and above the 5 target lesions should be identified as *non-target* lesions. Measurements must be provided for target measurable lesions, while presence or absence must be noted for non-target measurable and non-measurable disease.

New lesions: All measurable lesions not present at baseline up to a maximum of 2 lesions per organ 5 lesions in total, representative of all involved organs, should be identified as new target lesions (NTL). All other new lesions (not present at baseline) including any measurable new lesions over and above the 5 new target lesions should be identified as new lesions, non-target (NLNT). Measurements must be provided for NTL, while presence or absence must be noted for NLNT.

- a. **Complete Response (CR):** Complete disappearance of all target and non-target lesions (with the exception of lymph nodes mentioned below). No new lesions. No disease related symptoms. Any lymph nodes (whether target or non-target) must have reduction in short axis to < 1.0 cm. All disease must be assessed using the same technique as baseline.

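### Section 18.3 picks the partial-response cut on EFS and then tests it on OS in the same patients, so the OS test rejects too often by an amount that depends on a cut-point grid the plan does not state

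*Combined protocol and SAP*

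**What the plan says.** The Statistical Plan in Section 18.3 uses the minimum p-value approach, in the neoadjuvant arm, to "evaluate potential cut-points in percent viable tumor with respect to the outcome EFS for definitions of partial response". It mentions two existing proposals: "Some authors have proposed < 50% viable tumor, though others have argued that 40% necrosis should be considered a partial response". It lists no candidate cuts.

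The cut so chosen is carried to survival: "associations between pCR and pPR (using the definition derived using EFS) and the outcome of overall survival will be assessed with log-rank tests" and Cox models. That sentence ends on a comma. The same paragraph plans Cox models to "evaluate the association between the quantitative value of percent viable tumor and overall and event-free survival", and C-statistics for the quantitative and categorical versions.

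Related text:
- **Section 18.3, histologic assessment.** Percent viable is defined as "The percentage of the entire apparent tumor bed surface area occupied by viable tumor". Necrosis, melanosis and fibrosis are scored separately.
- **Sections 10.10 and 10.13.** EFS counts death from any cause. OS is time to death from the same origin, randomization.
- **Section 10.6.** A fixed pPR definition, under 50% viable, appears among what it calls "previously agreed upon standard definitions of pathologic response" from prior studies.
- **Section 1.2c.** Comparing pPR definitions and relating pathologic response to EFS and OS is a secondary objective.

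Sections 1.2, 11.4 and 18.3 give no significance level, hold-out sample, resampling or adjusted p-value for the pPR-OS test.

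**The concern.** Moving from EFS to OS looks like validation on a second endpoint, but it is not independent of the search. The patients are the same and the endpoints share deaths. Relapse, the main driver of EFS, usually comes before death. Part of whatever chance pattern made one cut the best for EFS therefore reappears in OS at that cut, and an ordinary log-rank or Cox test takes no account of this. If the minimum p-value method corrects the EFS p-value, that correction does not reach a separate OS test at the selected cut.

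At stake is how a secondary result is read. Section 18.3 presents the trial as an opportunity to standardize pathologic response evaluation. A cut tuned to these patients' EFS and then apparently supported by their OS could be taken as confirmed.

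**Working it through.** **No planned figure to reproduce.** The documents give no level, grid, event count or power for this test. The two-sided 15% in Section 11.2 belongs to the primary EFS test. A nominal two-sided 5% is assumed here.

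**Mechanism.** Let Z_E(c) and Z_O(c) be the log-rank statistics for EFS and OS at cut c. The plan takes c* = argmax |Z_E(c)| and then rejects if |Z_O(c*)| > 1.96. If viability is unrelated to either outcome, then in large samples Z_O(c*) = ρ·Z_E(c*) + √(1−ρ²)·ε. Here ε is standard normal and ρ is the correlation between the two statistics at one cut. Hence E[Z_O(c*)²] = 1 + ρ²(E[Z_E(c*)²] − 1). Selection makes E[Z_E(c*)²] exceed 1, so the OS test is inflated whenever ρ ≠ 0. A longer grid raises E[Z_E(c*)²] and a tighter EFS-OS link raises ρ.

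**Sample size.** 336 eligible (Section 11.3) / 2 = 168 per arm. Assuming 90% have surgery with a specimen, 168 × 0.90 = 151. Assumed pCR rates of 40%, 25% and 15% leave 91, 113 and 129 non-pCR patients. With the 85% submission target of Section 18.3, 168 × 0.85 = 143.

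**Other inputs.** EFS follows the cure models of Section 11.2 (30% susceptible with median 2.5 years, or 40% with median 2 years). The EFS data cut is 6 months after accrual (Section 11.3). Day-84 EFS events for patients who do not start adjuvant therapy (Section 10.10) are set at 0-20%. Assumed, not in the documents: the distribution of percent viable, post-relapse survival, and the grids. The two-cut grid is 50% and 60% viable and reads 40% necrosis as 60% viable. The others are 10-90% by 10 (nine cuts) and by 5 (17 cuts).

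**OS rejection (%) at the EFS-derived cut, no true association:**

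| Assumptions | Fixed 50% | 2 cuts | 9 cuts | 17 cuts |
|---|---|---|---|---|
| A. Broad range, 159 settings with at least 10 expected deaths | 3.9-5.8 | 4.8-8.6 | 5.9-21.0 | 6.7-24.9 |
| B. n=113, OS 3 years after the EFS data cut | 4.3-5.6 | 4.5-7.1 | 7.3-17.1 | 8.8-20.9 |
| C. n=151 with 25% pCR; pPR versus non-response | - | 5.0-7.2 | 7.9-17.5 | 9.6-21.1 |
| C. Same data; three groups (pCR/pPR/non-response) | - | 4.8-6.9 | 7.4-12.5 | 9.0-15.7 |

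- Over all 240 settings of A the medians are 4.8 (fixed), 5.9, 9.8 and 11.0. The excess over the fixed cut is 1.1, 5.0 and 6.2 points. The derived cut rejects more often than the fixed cut in 235/240 settings with two cuts and in 240/240 with nine or 17.
- EFS-OS link: in the 159 settings, nine cuts give 11-21% with no day-84 events and 6-10% with 20%.
- A further run with 143 evaluable patients and no day-84 events gives 9-29% with 17 cuts. The top is at 8-10 years of follow-up with short survival after the EFS event.
- Controls in that run: random cut 3.8-5.1%; OS made independent of EFS 4.1-5.3%. The excess therefore comes from selecting on a correlated endpoint. Raising n to 250 leaves it at 16.0%.

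**Estimates when viability truly predicts relapse** (54 settings, n=113). The nominal 95% interval for the OS hazard ratio covers the population value at the chosen cut in 93.3-97.6% (two cuts), 85.9-95.6% (nine), 83.5-95.2% (17) and 94.6-97.9% (fixed 50%). The median hazard ratio is off by -5 to +10%, 0 to +41%, +1 to +52% and -3 to +6%.

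**Remedy check.** A permutation test that repeats the EFS search and then the OS test brings rejection from 5.8-7.0% to 4.3-5.8% (two cuts), from 7.9-19.8% to 4.5-5.7% (nine) and from 8.4-23.7% to 4.2-5.4% (17).

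**The case against.** The strongest reply is that the plan names only two definitions. If only those are searched, the excess is about one percentage point, and the large figures need a grid that the text never mentions. This stands, and it rules out the reading that the OS test is badly inflated whatever is done. What remains is that the text refers to potential cut-points without limiting them. Treating 40% necrosis as 60% viable is itself an assumption, because necrosis is scored separately.

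Other points that stand, in whole or in part:
- The wording also fits a three-group test, where inflation is usually smaller.
- Valid OS tests already exist in the plan: pCR, and the Cox models on quantitative percent viable. A reader might infer that all the pathologic-response results, or even the primary comparison, are compromised. The documents do not support that, since none of those analyses uses the derived cut.
- The key sentence ends on a comma and the cited methods paper was not available, so an intended adjustment cannot be excluded. As written, the citation is attached to the EFS search.
- The permutation p-value addresses the joint null of no association with EFS or OS. It does not repair the derived cut's hazard ratio.
- Two neighbouring points are minor. The search adds about 0.01 (two cuts) to 0.02-0.04 (17 cuts) to the apparent EFS C-statistic. The difference between Section 10.6 (standard definitions from prior studies) and Section 18.3 (no consensus on pPR) is a tension of wording.

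**Conclusion.** The concern holds in conditional form. The planned OS test at the EFS-derived cut is anti-conservative, and the size depends on the unstated grid, the EFS-OS link and the comparison used. For pPR versus non-response at an assumed 5%, expect about 5-7% rejection with the two named definitions and roughly 7-21% with nine to 17 cuts, against about 5% for a fixed 50% cut. Values up to 25% or 29% need 17 cuts and a close EFS-OS link or long follow-up, and should not be read as the expected size. The direction is secure. The size rests on assumed post-relapse survival, viability distribution, pCR rate and level, none of which the documents give. This is a secondary analysis, worth correcting before the data are analyzed; the trial's main conclusion does not depend on it.

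**What to change.** In Section 18.3:
1. List the candidate cut-points in advance, say how the necrosis-based proposal maps to the scored quantities, and state whether the OS comparison is pPR versus non-response or three groups.
2. Use the fixed <50% viable definition of Section 10.6 for the main pPR-OS test.
3. Keep the EFS-derived cut for the objective of comparing definitions, but report its OS result as exploratory. Give a permutation p-value that repeats both the EFS search and the OS test.
4. State that the derived cut's OS hazard ratio and confidence interval are not corrected for selection, or give a bootstrap-corrected estimate.
5. Leave the pCR test and the quantitative Cox models as planned.

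The cost is a few sentences and a little programming. The derived cut will show less apparent significance. No new patients, data or changes to trial conduct are needed.
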